**D.11.5.1. Hypothesis 2a: Sleep BP on HBPM will provide an accurate estimate of sleep BP on ABPM.**

We will assemble a scatterplot of mean sleep SBP on HBPM versus ABPM and a intraclass correlation coefficient will be calculated. The statistical significance of the difference in mean sleep SBP on HBPM versus ABPM will be calculated using paired t-tests. The analysis will be repeated using sleep DBP on HBPM versus ABPM. We will create Bland-Altman plots showing the difference between sleep BP on HBPM versus ABPM by ABPM sleep BP level. We will calculate the percentage of participants who have a 10 mm Hg or larger absolute difference in their mean sleep SBP or a 5 mm Hg or larger absolute difference in their mean sleep DBP when measured by HBPM versus ABPM. Differences in mean sleep BP (SBP and DBP, separately) measured on HBPM versus ABPM will be calculated within age, race/ethnicity and sex sub-groupings. We will calculate the overall agreement and Kappa statistic between nocturnal hypertension on HBPM and ABPM, and test for a difference in prevalence using McNemar's test. We will compare differences in mean sleep SBP and DBP by randomization assignment using t-tests. If differences are statistically significant, analyses will include adjustment for randomization assignment.

**D.11.5.2. Hypothesis 2b: HBPM will be better tolerated than ABPM.** An overall score on the HBPM/ABPM tolerability questionnaire will be calculated by summing the scores on the eight Likert-type items after reverse coding positively-framed items (i.e., those with higher scores indicating better tolerability). Consistent with the approach of Viera, poor tolerance will be defined as an overall score  $\geq 75^{\text{th}}$  percentile on the results for ABPM. The cut-point identified for ABPM will be applied to define poor HBPM tolerability. Also, the percent of participants who report "pain", "skin irritation" and "bruising" from the ABPM device, and separately, the HBPM device will be calculated. The statistical significance of differences in responses to these items when wearing the HBPM and ABPM devices will be calculated using McNemar tests.

**D.11.6. Aim 3. Compare the associations of unattended versus attended clinic BP, unattended clinic BP versus awake BP on ABPM, and sleep BP on HBPM versus ABPM with two markers of end-organ damage, LVMI and ACR.**

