**D.12. Sample size/minimum detectable effects.**

[figure not shown]
**D.12.1. Aim 1.** Sample size and minimal detectable difference calculations were based on 80% statistical power and a two-sided alpha level of 5%. These calculations were performed using simulations and R version

3.3.2. We estimate that a sample size of 600 participants (630 enrolled participants with 30 participants [5%] not completing the study) will allow us to detect small but clinically relevant differences for each aim.

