**D.12.2.1. Minimum detectable effect size - hypothesis 2a.** We assumed a standard deviation of sleep SBP of 15 mm Hg and sleep DBP of 10 mm Hg when measured using ABPM and HBPM. Also, the correlation between sleep BP on ABPM and HBPM was assumed to be 0.5 for SBP and DBP. For this analysis, we are testing that mean sleep BP is equivalent when measured by HBPM and ABPM. A sample size of 600 participants will provide 80% statistical power to exclude an absolute mean difference equal to or larger than 2.1 mmHg for SBP or 1.4 mmHg for DBP comparing ABPM versus HBPM exists. In a sub-group of 160 participants, we can exclude an absolute mean difference equal to or larger than 4.0 mmHg for SBP or 2.7 mmHg for DBP. If the correlation of sleep BP on ABPM and HBPM is higher (e.g., 0.7 or 0.9), we can exclude smaller absolute differences. A sample size of 600 participants will provide narrow confidence intervals for the observed agreement and kappa statistic for nocturnal hypertension comparing HBPM and ABPM. For example, the 95% confidence interval for an observed agreement of 80% and 90% would be 77%-83% and 88%-92%, respectively, and for a kappa statistic of 0.6 and 0.8 would be 0.54-0.66 and 0.75-0.85, respectively.

**D.12.2.2. Minimum detectable effect size - hypothesis 2b.** By definition, 25% of participants will have poor tolerance to ABPM. The minimum detectable difference in the prevalence of poor tolerance comparing HBPM versus ABPM depends on the percentage of participants who have poor tolerance to one method but not to the other. With a sample size of 600 participants, we can detect a difference in poor tolerance of ABPM and HBPM of 3% (25% versus 22%) if 20% of participants report poor tolerance to both methods (e.g., if 5% has poor tolerance to ABPM but not to HBPM, and 2% has poor tolerance to HBPM but not to ABPM). Assuming 5% of participants experience bruising with both ABPM and HBPM, we will have 80% power to detect a difference in the prevalence of bruising of 3% or larger comparing ABPM and HBPM.

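### Hypothesis 2b analyses the overall tolerability score only as poor/not poor at the ABPM 75th percentile, so its 80% power depends on very few discordant participants

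*Combined protocol and SAP*

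**What the plan says.** Every participant wears both devices, so each has two tolerability scores. D.11.5.2 forms the overall score by summing eight Likert-type items, defines poor tolerance as a score at or above the ABPM 75th percentile, citing consistency with an earlier study, and carries the same threshold over: "The cut-point identified for ABPM will be applied to define poor HBPM tolerability". It also plans McNemar tests for pain, skin irritation and bruising.

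D.12.2.2 powers the binary comparison. It starts from "By definition, 25% of participants will have poor tolerance to ABPM" and claims that 600 participants can detect 25% versus 22% "if 20% of participants report poor tolerance to both methods", giving as an example "if 5% has poor tolerance to ABPM but not to HBPM, and 2% has poor tolerance to HBPM but not to ABPM". The same section separately powers bruising.

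The Analysis Plan treats tolerability in item 6 of its statistical analysis and in Table 8. There the single items are counted as occurring with ABPM only, HBPM only, both or neither. It contains no overall score, no percentile cut and no tolerability test.

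**The concern.** Hypothesis 2b says that HBPM is better tolerated than ABPM. The most direct test of that with an overall score is the within-person difference. After the cut, a participant informs the comparison only if the two devices fall on opposite sides of one point; a clear improvement that stays on one side of it counts for nothing. The point itself is set by the sample.

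Hypothesis 2a, in the same aim, is handled differently: D.11.5.1 tests the paired mean difference in sleep BP and reports the proportion beyond a threshold in addition. For the overall score, Hypothesis 2b has the threshold alone.

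At stake is whether the overall-score analysis could detect a modest tolerability advantage if more participants are discordant than D.12.2.2 assumes.

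**Working it through.** **Inputs from the documents.** n = 600 pairs; 25% poor with ABPM, 22% with HBPM; 20% poor with both; discordant cells p10 = 0.05 and p01 = 0.02 (D.12.2.2). Two-sided alpha 5% and 80% power are stated under D.12.1 and taken here to apply to Aim 2.

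**Step 1: the plan's own figure.** With d = p10 − p01 and s = p10 + p01, McNemar power by the normal approximation is Φ[(d√n − 1.96√s) / √(s − d²)].

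Here d = 0.03 and s = 0.07, so (0.03 × √600 − 1.96 × √0.07) / √(0.07 − 0.0009) = 0.2163 / 0.2629 = 0.823, and power = **0.795**. The number of pairs for 80% is 609. The uncorrected chi-square version gives 0.809 and the exact version 0.766. The stated 80% reproduces. It rests on 0.07 × 600 = 42 discordant participants.

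**Step 2: the same shift on the full score.** The documents give no SD, distribution or correlation for the score. Assume bivariate-normal scores with equal SDs and a pure location shift. Moving from 25% to 22% above the cut is a shift of z(0.78) − z(0.75) = 0.7722 − 0.6745 = 0.098 SD. For each proportion poor on both, solve for the correlation r that reproduces the cells. Paired-test power is then Φ[0.098 × √600 / √(2(1 − r)) − 1.96].

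| Poor on both | p10, p01 | Implied r | Power with cut | Power, full score |
|---|---|---|---|---|
| 20% (plan) | 0.05, 0.02 | 0.964 | 0.795 | >0.999 |
| 15% | 0.10, 0.07 | 0.768 | 0.43 | 0.94 |
| 12% | 0.13, 0.10 | 0.578 | 0.33 | 0.74 |
| 10% | 0.15, 0.12 | 0.424 | 0.29 | about 0.60 |

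**Step 3: larger shifts** (n = 600, same model).

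| Shift | r | Cut | Full score | Gap, points |
|---|---|---|---|---|
| 0.20 SD | 0.5 | 0.836 | 0.998 | 16.3 |
| 0.20 SD | 0.62 | 0.882 | >0.999 | 11.8 |
| 0.20 SD | 0.7 | 0.915 | >0.999 | 8.5 |
| 0.25 SD | 0.5 | 0.952 | >0.999 | 4.8 |
| 0.25 SD | 0.7 | 0.984 | >0.999 | 1.6 |

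**Step 4: dependence on normality.** In simulation at r = 0.7 and the 0.098 SD shift, the Wilcoxon signed-rank test had power 0.85, against 0.87 for the t-test. A coarse 10-level score with 40% of ABPM scores at the floor, simulated with 2,000 replicates, gave Wilcoxon power of about 0.79 against 0.43 for the cut at 15% poor on both, and 0.48 against 0.29 at 10%. The gap narrows but remains.

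**Step 5: is 7% discordance plausible?** Table 8 gives single-item discordance out of 603: pain (160 + 37)/603 = 32.7%, irritation (178 + 26)/603 = 33.8%, bruising (84 + 19)/603 = 17.1%, sleep interference (124 + 56)/603 = 29.9%. Ten of the 12 items lie between 15% and 37%; their tetrachoric correlations run from 0.12 to 0.74, median 0.62. Single items are noisier than a sum, so this is only indicative. At r = 0.62 and the 0.098 SD shift, the cut has about 35% power and the full score about 78%.

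**The case against.** The strongest case against has five parts.

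- **The plan's power statement is right.** This stands. A reader might infer that D.12.2.2 is miscalculated, or that the cut discards most of the power. The documents support neither: at the plan's own inputs about 80% power remains.
- **The loss matters only for a small effect.** This largely stands. The gap is wide at 0.098 SD and under 5 points at 0.25 SD. But 0.098 SD is the normal-score equivalent of the 3-point difference that D.12.2.2 chose.
- **Hypothesis 2b does not rest on the cut alone.** This stands. Pain, irritation and bruising have their own planned McNemar tests, and bruising is also powered. Table 8 shows large single-item differences (pain 160 versus 37, uncorrected McNemar chi-square 76.8), so the documents do not support an inference that the study could not show a tolerability difference.
- **The cut follows earlier work and a percentage is easy to read.** This is fair, and it is a reason to keep the percentage as a secondary result. It is not a reason to leave the score itself unanalysed.
- **The score may not be computable as defined.** This stands and shapes the fix. D.8.5 describes eight Likert-type items and gives sleep interference as its example, on a 0 to 10 scale, with pain as a yes/no example. The questionnaires in the manual ask sleep interference as No/Yes, and the HBPM form grades pain from none to a lot. The ABPM form also has a daytime-removal item that the HBPM form lacks.

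**Conclusion.** The point holds as one of efficiency and of fit to the hypothesis, not as an error in the power calculation. The overall-score endpoint is dichotomised, no paired analysis of the uncut score is specified, and 80% power is reached only if about 7% of participants are discordant. For the 3-point difference, power with the cut falls to about 29% to 43% when 10% to 15% are poor on both devices, against about 60% to 94% for the full score.

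These figures assume bivariate-normal scores, equal SDs and a pure shift; skew, ties or floor effects would change them. The direction persisted in the floored simulation, but the size cannot be fixed from the documents. In addition, the Analysis Plan carries neither the score nor a tolerability test, so D.11.5.2 and Table 8 need reconciling in any case.

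**What to change.** 1. In D.11.5.2, make the overall-score analysis for Hypothesis 2b the within-person difference (HBPM minus ABPM), by a paired t-test or Wilcoxon signed-rank test with a 95% CI. Build the score from the graded items common to both questionnaires as collected, and list those items.
2. Keep the proportion at or above the ABPM 75th percentile as a secondary result, and keep the planned McNemar tests of pain, irritation and bruising.
3. In D.12.2.2, restate the overall-score calculation as a detectable standardised mean difference over a stated range of within-person correlations.
4. Add the same analysis to item 6 and Table 8 of the Analysis Plan, labelled as added after the item-level results were tabulated.

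Cost: wording changes, a short item-mapping exercise and one paired test, with no new data collection. The downside is that the main overall-score result becomes a score difference, which is less familiar than a percentage, although the percentage is still reported.

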**D.12. Sample size/minimum detectable effects.**

[figure not shown]
**D.12.1. Aim 1.** Sample size and minimal detectable difference calculations were based on 80% statistical power and a two-sided alpha level of 5%. These calculations were performed using simulations and R version

3.3.2. We estimate that a sample size of 600 participants (630 enrolled participants with 30 participants [5%] not completing the study) will allow us to detect small but clinically relevant differences for each aim.

#### D.12.1.1. Sample size considerations for hypothesis 1a.

**Figure 4** shows the minimal detectable difference in differences with awake ABPM comparing unattended vs attended clinic BP. With 600 participants we can detect that the absolute difference with awake ABPM is 1.5 and 1.2 mm Hg smaller for unattended vs attended clinic BP assuming a correlation of 0.5 and 0.7, respectively between clinic BP and awake BP on ABPM. In a sub-group of 160 participants (e.g., African Americans), we can detect that the absolute difference with awake ABPM is 3.1 and 2.4 mm Hg smaller for unattended vs. attended clinic BP.

Smaller absolute differences can be detected if the correlation between attended and awake BP is higher.

**D.12.1.2. Sample size considerations for hypothesis 1b.** If 85% of participants have the same concordance/discordance status for both comparisons (i.e., attended clinic hypertension versus awake hypertension and unattended clinic hypertension versus awake hypertension), enrollment of 600 participants will provide 80% statistical power to detect a difference of 5% in the two overall agreements (e.g., 70% vs. 75%). If the expected agreement is 50%, we will have an 80% statistical power to detect a difference between Kappa statistics of 0.4 and 0.5 using a two-sided alpha level of 0.05. With 600 participants and a phenotype prevalence of 15%, we can detect a difference in the prevalence of 4% when clinic BP is measured unattended versus attended. In a sub-group of 160 participants, we can detect a difference of 8%. Based on these estimates, we chose to enroll 630 participants in the proposed study (n=600 with complete data).

#### D.12.2. Aim 2

**D.12.2.1. Minimum detectable effect size - hypothesis 2a.** We assumed a standard deviation of sleep SBP of 15 mm Hg and sleep DBP of 10 mm Hg when measured using ABPM and HBPM. Also, the correlation between sleep BP on ABPM and HBPM was assumed to be 0.5 for SBP and DBP. For this analysis, we are testing that mean sleep BP is equivalent when measured by HBPM and ABPM. A sample size of 600 participants will provide 80% statistical power to exclude an absolute mean difference equal to or larger than 2.1 mmHg for SBP or 1.4 mmHg for DBP comparing ABPM versus HBPM exists. In a sub-group of 160 participants, we can exclude an absolute mean difference equal to or larger than 4.0 mmHg for SBP or 2.7 mmHg for DBP. If the correlation of sleep BP on ABPM and HBPM is higher (e.g., 0.7 or 0.9), we can exclude smaller absolute differences. A sample size of 600 participants will provide narrow confidence intervals for the observed agreement and kappa statistic for nocturnal hypertension comparing HBPM and ABPM. For example, the 95% confidence interval for an observed agreement of 80% and 90% would be 77%-83% and 88%-92%, respectively, and for a kappa statistic of 0.6 and 0.8 would be 0.54-0.66 and 0.75-0.85, respectively.

**D.12.2.2. Minimum detectable effect size - hypothesis 2b.** By definition, 25% of participants will have poor tolerance to ABPM. The minimum detectable difference in the prevalence of poor tolerance comparing HBPM versus ABPM depends on the percentage of participants who have poor tolerance to one method but not to the other. With a sample size of 600 participants, we can detect a difference in poor tolerance of ABPM and HBPM of 3% (25% versus 22%) if 20% of participants report poor tolerance to both methods (e.g., if 5% has poor tolerance to ABPM but not to HBPM, and 2% has poor tolerance to HBPM but not to ABPM). Assuming 5% of participants experience bruising with both ABPM and HBPM, we will have 80% power to detect a difference in the prevalence of bruising of 3% or larger comparing ABPM and HBPM.

**Table 7. Minimal detectable correlation coefficients between BP measurements and LVMI.**

Correlation between standard and alternative BP measurements †	Correlation coefficient between standard BP measurements and LVMI		
	0.30	0.50	0.60
0.5 (n=600)	0.11	0.09	0.08
0.7 (n=600)	0.08	0.07	0.07
0.5 (n=160)	0.18	0.15	0.13
0.7 (n=160)	0.14	0.12	0.11

80% power; 2-tailed  $\alpha=0.05$ . †For example, standard measurement may be attended BP and alternative is unattended BP.

**D.12.3. Aim 3.** **Table 7** shows minimum detectable differences in correlation coefficients for hypotheses 3a, 3b and 3c with the full population (n=600) or a sub-group (n=160) of participants. For example, if the correlation between attended and unattended clinic BP is 0.5, and the correlation between attended BP and LVMI is 0.3,

we will have 80% power to detect a difference in the correlation between attended and unattended BP and LVMI of 0.11 or larger (e.g., 0.30 versus 0.41). Detectable differences in the correlation coefficients will be modestly larger in sub-groups of 160 participants. The detectable differences will be smaller if the correlation between attended and unattended clinic BP is higher (e.g., 0.7).

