**Hypothesis 3a:** The association with end-organ damage will be stronger for unattended vs. attended clinic BP.

**Hypothesis 3b:** The association with end-organ damage will be similar for unattended clinic and awake BP.

**Hypothesis 3c:** The association with end-organ damage will be similar for sleep BP by HBPM and ABPM.

Below we describe the analysis plan for testing Hypothesis 3a. The analysis plan will be identical for Hypotheses 3b and 3c. We will calculate the intraclass correlation coefficients between (1) attended clinic BP and (2) unattended clinic BP with LVMI. The statistical significance of the difference in the correlation coefficients will be calculated using the Fisher r-to-z transformation accounting for the within-person correlation between unattended and attended BP measurements. Also, the association between clinic BP, measured unattended and attended, separately, and LVMI will be calculated using linear regression. For these models, clinic BP will be modeled in categories, using restricted quadratic splines, and, if appropriate, as a continuous variable (e.g., per 10 mm Hg higher SBP). Two levels of adjustment will be performed as described in **Section D.11.2.**

For secondary testing of Hypothesis 3, we will model the outcome of LVH defined as an  $\text{LVMI} \geq 96 \text{ g/m}^2$  in women and  $\text{LVMI} \geq 116 \text{ g/m}^2$  in men using Poisson regression with robust standard errors and two levels of adjustment (**Section D.11.2**). The analyses will be repeated for the outcome of the ACR. When modeled as a continuous variable, ACR will be log-transformed due to its skewed distribution. As a dichotomous variable, albuminuria will be defined as an sex/race-adjusted  $\text{ACR} > 25 \text{ mg/g}$ .

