**D.14. Translation into practice.** Upon completion of the study, we will conduct a stakeholders meeting with clinical leaders in the field of hypertension to develop a statement on the use of unattended BP and sleep HBPM assessment in clinical practice. This meeting will include committee members from the AHA's Scientific Statement on BP measurement, which [name] and [name] co-chair. [name] is director of the Lister Hill Center for Health Policy at UAB and will use center funds for this meeting.

**D.15. Reproducibility and transparency.** We will post the aims, methods, and original analytical plan prior to data collection on the Open Science Framework website, which is hosted by the recently founded Center for Open Science (funded in part by the NIH and the National Science Foundation; <https://osf.io>), and is open to the public to view. Once the proposed study has been completed and before data analyses are initiated, we will post the code for derivation of study variables and the final sample size (with a flow diagram on how the final sample was derived). For each abstract and manuscript, all coding will be carefully labeled and linked to the final versions of each document. None of the posted documents will contain participant identifiers.

**D.16. Consideration of sex and other biological variables.** We will make every effort to recruit equal numbers of men and women. As noted above, we will conduct exploratory analyses stratifying by age group, sex, and race/ethnicity (white, African American, and Hispanic; a minimum of 160 each).

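### The six n=160 entries in the Aim 3 power table (Table 7) do not follow from its stated inputs: power at the printed differences is about 68 to 72%, not 80%

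*Combined protocol and SAP*

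**What the plan says.** Section D.12.3 refers to Table 7 for minimum detectable differences in correlation coefficients for hypotheses 3a to 3c, "with the full population (n=600) or a sub-group (n=160) of participants". The table footnote, "80% power; 2-tailed" alpha 0.05, applies to every row and matches the general statement in D.12.1. The columns are correlations of the standard BP measure with LVMI of 0.30, 0.50 and 0.60. The rows are correlations between the standard and alternative BP measures of 0.5 and 0.7. The worked example sets the direction: the alternative measure has the higher correlation (0.30 versus 0.41 at n=600).

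The test is given in D.11.6: the "Fisher r-to-z transformation accounting for the within-person correlation between unattended and attended BP measurements".

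On sub-groups the text says only that "Detectable differences in the correlation coefficients will be modestly larger in sub-groups of 160 participants". The figure of 160 comes from D.4.2, which asks for at least 160 white, 160 African American and 160 Hispanic participants and gives statistical power as the reason.

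**The concern.** A detectable difference on the Fisher z scale is inversely proportional to the square root of n−3. Going from 600 to 160 should therefore stretch it by about √(597/157) = 1.95, and slightly less on the correlation scale. The n=160 entries are only 1.63 to 1.71 times the unrounded n=600 values derived under Working (for example 0.18/0.1052 = 1.71). Either the entries are too small or they were computed with inputs other than those stated.

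Table 7 is the plan's only statement of what a stratum of 160 can show for Aim 3. If it is too optimistic, a null result in one racial or ethnic group would be read as more informative than it is: the chance of missing the stated difference would be nearer 30% than 20%.

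**Working it through.** **Inputs, all from the plan.** Power 80% and two-sided alpha 0.05 (D.12.1 and the Table 7 footnote); n = 600 and 160; between-measure correlation c = 0.5 and 0.7; standard-measure correlation with LVMI r1 = 0.30, 0.50 and 0.60; alternative r2 = r1 + d.

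**Formula.** For two dependent correlations sharing one variable (Steiger form, pooled correlation):

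- m = (r1 + r2)/2
- s = [c(1−2m²) − ½m²(1−2m²−c²)] / (1−m²)²
- Z = [atanh(r2) − atanh(r1)] × √[(n−3)/(2−2s)]
- Power = Φ(Z − 1.960). The detectable d is the value at which Z = 1.960 + 0.842 = 2.802.

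**Step 1: reproduce the n=600 rows.** First cell, c = 0.5, r1 = 0.30, d = 0.1052: m = 0.3526, s = 0.4493, difference in atanh = 0.1203, multiplier √(597/1.1014) = 23.28, Z = 2.80. So d = 0.105, printed 0.11.

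| n=600 | r1=0.30 | r1=0.50 | r1=0.60 |
|---|---|---|---|
| c=0.5, computed | 0.1052 | 0.0907 | 0.0798 |
| c=0.5, printed | 0.11 | 0.09 | 0.08 |
| c=0.7, computed | 0.0826 | 0.0725 | 0.0651 |
| c=0.7, printed | 0.08 | 0.07 | 0.07 |

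All six agree after rounding, so the method matches this half of the table.

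**Step 2: the same formula at n=160.** First cell at the printed d = 0.18: m = 0.39, s = 0.4368, difference in atanh = 0.5230 − 0.3095 = 0.2135, multiplier √(157/1.1264) = 11.81, Z = 2.52, power = Φ(0.56) = 0.712.

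| n=160 | r1=0.30 | r1=0.50 | r1=0.60 |
|---|---|---|---|
| c=0.5, computed | 0.1987 | 0.1675 | 0.1453 |
| c=0.5, printed | 0.18 | 0.15 | 0.13 |
| Power at printed value | 71.2% | 69.7% | 69.2% |
| c=0.7, computed | 0.1576 | 0.1364 | 0.1211 |
| c=0.7, printed | 0.14 | 0.12 | 0.11 |
| Power at printed value | 69.7% | 68.4% | 71.2% |

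None of the six agrees. The computed values exceed the printed ones by 10% (0.1211/0.11) to 14% (0.1364/0.12).

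**Step 3: is it rounding or the choice of test?**

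- Adding 0.005 to every printed entry, the most that rounding allows, raises power only to 72–76% across the pooled and unpooled (Dunn–Clark) forms.
- The Dunn–Clark form gives 0.1978/0.1670/0.1450 and 0.1570/0.1358/0.1206, with power 68.8–71.6% at the printed values. The Williams test, the most favourable of the dependent-correlation tests tried, gives 69.7–72.5%.
- D.12.1 says the plan's calculations used simulation. Simulating trivariate normal data at n=160, 20,000 runs per cell, gives 72.2/70.2/69.8% and 70.5/68.5/71.5% at the printed differences.

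**Step 4: what would produce the printed entries?**

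- A one-sided 5% test at n=160 gives 0.178/0.151/0.131 and 0.141/0.122/0.109, which round to all six. It contradicts the footnote, and at n=600 it gives 0.094/0.081/0.071 and 0.073/0.065/0.058, which do not fit.
- A two-sided test at n=200 gives 0.179/0.151/0.132 and 0.141/0.123/0.109, which also round to all six. It contradicts the row label.

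No single set of inputs tried yields the whole table.

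**The case against.** The strongest reply is that the label, not the entries, may be wrong. The plan gives 160 as a floor (D.4.2 and D.16). The planned enrolment table allots 210 to each of the non-Hispanic Black, non-Hispanic White and Hispanic groups. With 600 of 630 completing, that is 210 × 600/630 = 200 per group, and age tertiles of 600 are also 200. At n=200 the printed differences carry 78–81% power. This is a plausible origin, but the plan does not state it. Table 7, the text of D.12.3 and the other sub-group calculations (D.12.1 and D.12.2) all use 160, and D.4.2 ties that number to power. As labelled, the entries are wrong.

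The second reply is that little turns on it, and that largely stands. The gap is 0.01 to 0.02 on the correlation scale. D.16 says "we will conduct exploratory analyses stratifying by age group, sex, and race/ethnicity", D.11.6 specifies no sub-group analysis for Aim 3, and items 7 to 12 of the Analysis Plan contain no strata.

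The between-measure correlations also differ from the planning values. From the SDs and confidence intervals in Analysis Plan Tables 2 and 7, the systolic correlations are about 0.95 (attended with unattended), 0.76 (unattended with awake ABPM) and 0.67 (sleep HBPM with ABPM). For the first, the SD of the difference is 0.30/1.96 × √569 = 3.65, so r = (12.1² + 11.9² − 3.65²)/(2 × 12.1 × 11.9) = 0.95. At those values and r1 = 0.30, detectable differences at n=160 would be about 0.06, 0.14 and 0.16. This limits the practical effect but does not make the planning table right on its own assumptions.

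**Conclusion.** The concern holds. Under the inputs the plan states, the n=160 rows claim 80% power where the design gives 68 to 72%, an overstatement of 8 to 12 percentage points, and the error is optimistic in all six cells. The description of the sub-group differences as modestly larger is also generous: in the worked example the detectable difference goes from 0.105 to 0.199, a factor of 1.9.

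The result rests on a two-sided 5% test, a Fisher z comparison of dependent correlations, and an alternative measure with the higher correlation. All three come from the plan, and its n=600 rows confirm them. The cause of the mismatch is not known.

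The n=600 rows and the main Aim 3 analyses are unaffected. So is the enrolment target, which D.12.1.2 derives from the Aim 1 calculations: "Based on these estimates, we chose to enroll 630 participants in the proposed study".

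**What to change.** Keep the n=160 label and two-sided alpha, and replace the two rows:

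- correlation 0.5: 0.20, 0.17, 0.145 (the last is given to three decimals because it sits on a rounding boundary)
- correlation 0.7: 0.16, 0.14, 0.12

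Amend the sentence on sub-groups to give a figure: for the worked example, a difference of about 0.20 at n=160 (0.30 versus 0.50) beside the 0.11 at n=600. The n=600 example itself is correct and should stay. If the sponsor's records show that another alpha or n was used for these rows, that should be stated as well.

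The cost is six table entries and one sentence. Design, sample size and main analyses do not change.
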